6.5.9 Ad-hoc Analyses

Other ad hoc analyses, defined as analyses not detailed in this SAP, may be done in addition to those specified here as the primary and secondary papers are developed. These will be clearly labeled in any publication as ad hoc analyses motivated by our findings as we completed the planned data analyses.

6.6 Missing Data

No imputation for missing data will be done.

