5 TRIAL POPULATION

5.1 Screening population

All infants born at 33 0/7 to 35 6/7 weeks gestation and ≥ 1500 grams are screened for study entry if they are admitted to the NICU with an admitting diagnosis of acute perinatal asphyxia, neonatal depression, encephalopathy and/or fetal acidemia at less than 6 hours of age. All these infants at < 6 hours of age are evaluated by clinical and biochemical criteria and further assessed by neurological examination. Both inborn and outborn infants are evaluated. From this population, babies are screened for inclusion in the trial using the following eligibility criteria.

Eligibility

Inclusion criteria

Infants 33 0/7 to 35 6/7 weeks GA (best obstetrical estimate) and ≥ 1500 grams birth weight (to minimize potential difficulties placing esophageal probe) who meet clinical, biochemical and neurologic criteria for moderate to severe NE in this GA range at ≤ 6 hours age:

1) Biochemical:

Cord gas or if unavailable, blood gas within first hour of life with $\text{pH} \leq 7.00$ or base deficit (BD) ≥ 16 mEq/L, OR

2) Clinical in the absence of blood gas results or Clinical with more modest fetal acidemia (cord or 1st hour of life blood gas with a pH of 7.01-7.15 or BD > 10.0 to 15.9mEq/L):

a) Acute perinatal event (e.g., abruptio placenta, cord prolapse, uterine rupture, maternal cardiac or respiratory arrest, severe FHR abnormality such as variable or late decelerations,) AND

b) Requirement for positive pressure ventilation for apnea OR poor respiratory effort since birth for at least 10 minutes OR 10-minute Apgar score ≤ 5

AND

3) Neurologic:

Clinical Seizures OR modified Sarnat score with moderate or severe abnormalities in at least 3 of the 6 categories; at least one must be altered level of consciousness (lethargy or stupor/coma) as determined by a certified examiner.

All infants who meet criteria for potential inclusion should undergo standard neurologic exam as for infants ≥ 36 wks GA being considered for hypothermia, with findings recorded.

Criteria for exclusion in hypothermia trial

1) Receipt of paralytic agent or sufficient sedative or analgesic agent that is considered by the examiner to confound the qualifying neurologic exam

2) Etiology of NE not likely to be hypoxic-ischemic in origin

3) Major congenital anomaly that may confound outcome

4) Considered to be moribund and will not be receiving full intensive care

- 5) Equipment and/or appropriate staff not available

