- Received cord blood gas (*Binary, PH05: E.1, PH5CBGO, will be used in the construction of a derived variable containing cord blood gas information if non-missing and <1 hour of age information if cord blood gas information is missing and <1 hour of age information is non-missing. Stated another way: select cord gas if both cord gas and 1 hr gas are available and select 1 hr gas if cord not available. These variables are an intermediate step. See cord or postnatal variables below for variables that will actually get used in reports.*)
 - Source (*Multiple level discrete, PH05: E.1.a, PH5CBS*)
 - pH (*Continuous, PH05: E.1.b, PH5CBPH*)
 - PCO₂ (mmHg) (*Continuous, PH05: E.1.c, PH5CBPCO*)
 - PO₂ (mmHg) (*Continuous, PH05: E.1.d, PH5CBP02*)
 - HCO₃ (mEq) (*Continuous, PH05: E.1.e, PH5CBHCO*)
 - Base deficit (*Continuous, PH05: E.1.f, PH5CBBD*)
- Postnatal blood gas obtained at <1 hour of age (*Binary, PH05: E.2, PH5PNBGO, will be used in the construction of a derived variable containing cord blood gas information if non-missing and <1 hour of age information if cord blood gas information is missing and <1 hour of age information is non-missing. Stated another way: select cord gas if both cord gas and 1 hr gas are available and select 1 hr gas if cord not available. These variables are an intermediate step. See cord or postnatal variables below for variables that will actually get used in reports*)
 - Source (*Multiple level discrete, PH05: E.2.a, PH5PGS*)
 - pH (*Continuous, PH05: E.2.d, PH5PGPH*)
 - PCO₂ (mmHg) (*Continuous, PH05: E.2.e, PH5PGPCO*)
 - PO₂ (mmHg) (*Continuous, PH05: E.2.f, PH5PGPO2*)
 - HCO₃ (mEq) (*Continuous, PH05: E.2.g, PH5PGHCO*)
 - Base deficit (*Continuous, PH05: E.2.h, PH5PGBD*)
- Cord or postnatal (<1 hour of age) blood gas (*Combination of appropriate blood gas variables from the above two blood gas groups. Use Cord variable if non-missing and use <1 hour variable if cord variable is missing and <1 hour variable is non-missing. Stated another way: select cord gas if both cord gas and 1 hr gas are available and select 1 hr gas if cord not available. These variables will actually be the variables used in reports covering cord or postnatal blood gas.*)
 - pH (*Continuous*)
 - PCO₂ (mmHg) (*Continuous*)
 - PO₂ (mmHg) (*Continuous*)
 - HCO₃ (mEq) (*Continuous*)

- Base deficit (*Continuous*)
- Maternal baseline variables
 - Mother's age (*Continuous, PH04: A.1, PH4MAGE*)

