- Mode of delivery (*Multiple level discrete, PH04: F.1, PH4FNMOD*)

Note: The amount of missing data will be indicated in the Tables.

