The prior for the random center effects will be Normal centered at 0, and the hyperprior for the standard deviation of the random center effect will be specified in Section 6.5.3. Any baseline covariates that are added to the model (in sensitivity analyses to adjust for important unbalanced baseline covariates) will either be coded using 0/1 indicator variables, sets of indicator variables, or as centered continuous covariates. Priors for these other to-be-determined covariates are specified in Section 6.5.3. Post processing will be used to get posterior approximations of relative risk and risk differences due to treatment. The logistic model will be fit to the data, then for each infant, the model parameter chains will be used to estimate the within subject posterior relative risk and risk difference which will equal hypothermia divided by normothermia and hypothermia minus normothermia respectively. A within subject estimate of relative risk will be calculated by setting

the treatment variable value to hypothermia, estimating the probability of outcome for all infants, repeating the same process after setting the treatment variable to normothermia then dividing the two probabilities of outcome for all infants, hypothermia over normothermia. A within subject estimate of risk difference will be calculated by setting the treatment variable value to hypothermia, estimating the probability of outcome for all infants, repeating the same process after setting the treatment variable to normothermia then subtracting the two probabilities of outcome for all infants, hypothermia minus normothermia. Since the parameter chains will contain at least 120,000 samples, each infant will contribute at least 120,000 samples for the approximation of the within subject relative risk posterior and the within subject risk difference posterior. Using all samples of relative risk and risk differences from all infants to approximate the posteriors, the mean estimate of relative risk and risk difference will be calculated as well as, 95% credible intervals of mean relative risk and risk difference. Finally, posterior probabilities of benefit due to hypothermia from both relative risk and risk differences will be used as summary statistics. Differences in the relative risk and risk difference posteriors will be reflected upon to better understand the estimated treatment effect.

For count outcomes like days or duration, y_{ij} , the main covariates will have the form:

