6.5.7 Sensitivity Analysis

In addition to adjusting for level of encephalopathy and center as a random effect, sensitivity analyses may be completed, at the discretion of the Preemie Hypothermia subcommittee, by selecting baseline covariates that differ across the two treatments. These covariates will be selected from those covariates listed in section 5.3. This analysis will only be completed for the primary outcome (death or moderate to severe disability at 18-22 months corrected age) and Death. These sensitivity analyses will be based on the FAS population.

In addition to the FAS population-based analysis, exploratory PP analyses may be done using the PP population on the primary or secondary outcomes at the discretion of the Preemie Hypothermia subcommittee, if the FAS analysis of the primary or secondary outcome results in any clinically notable findings.

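### The blanket no-imputation rule makes no exception for baseline covariates, so an adjusted analysis using an incomplete covariate cannot run on the FAS that SAP 6.5.7 names

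*SAP*

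**What the plan says.** - **Missing data (SAP 6.6).** The whole section reads "No imputation for missing data will be done". It does not distinguish outcomes from covariates.
- **Eligibility (SAP 5.1).** The second qualifying route is "Clinical in the absence of blood gas results or Clinical with more modest fetal acidemia", so an infant can enter with no gas result.
- **Blood gas covariate (SAP 5.3).** The derivation is "Use Cord variable if non-missing and use <1 hour variable if cord variable is missing and <1 hour variable is non-missing". When neither gas exists, the derived pH, PCO₂, PO₂, HCO₃ and base deficit are all missing.
- **Expected gaps (SAP 5.3).** "The amount of missing data will be indicated in the Tables". This is a reporting rule and does not tell the analyst what to do in a model.
- **Choice of adjustment covariates (SAP 6.5.7).** They are chosen "by selecting baseline covariates that differ across the two treatments", and "These covariates will be selected from those covariates listed in section 5.3".
- **Coding (SAP 6.5.1).** Added covariates are "coded using 0/1 indicator variables, sets of indicator variables, or as centered continuous covariates". The blood gas items are typed as continuous, and no provision is made for a missing continuous value.
- **Population (SAP 6.5.7).** "These sensitivity analyses will be based on the FAS population". SAP 4.3 defines the FAS by randomization and an ascertained primary outcome; completeness of covariates plays no part.
- **Secondary outcomes (SAP 6.5.5).** If a secondary analysis is covariate-adjusted, only the adjusted version is run.

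**The concern.** A covariate sensitivity analysis is meant to show whether adjustment changes the treatment estimate. That reading requires the same infants in both fits. If the adjusted model loses infants because a covariate is blank, a change in the estimate may reflect the covariate, the change of sample, or both.

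For blood gas the lost infants share a feature: they have no cord or first-hour result, and some were enrolled on the clinical criteria for that reason. The adjusted estimate then describes the infants with a recorded gas, while the SAP labels it an FAS result. In a trial whose size was set by what could be enrolled (SAP 3.4), dropping infants whose outcome and treatment are both known also gives up precision that could be kept.

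**Working it through.** The SAP states no missing-covariate rate or complete-case sample size, so there is no figure to reproduce. The check has a textual part and a part conditional on an assumed rate.

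**Do the provisions fit together?**

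1. SAP 5.1 admits infants with no blood gas.
2. SAP 5.3 leaves the derived gas covariate missing for an infant with neither a cord nor a first-hour value.
3. SAP 6.5.2, 6.5.5 and 6.5.7 allow that covariate to be selected.
4. SAP 6.5.1 enters it as a centered continuous term, which has no value for that infant.
5. SAP 6.6 rules out supplying one.
6. The infant therefore drops out of the likelihood. SAP 4.3 still counts the infant in the FAS if the primary outcome is known, and 6.5.7 says the analysis uses the FAS.

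Steps 5 and 6 conflict whenever a selected continuous covariate has a gap. The SAP does not use the term complete case; deletion is inferred because nothing else is specified.

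**How much is lost?**

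Inputs: N = 168 (SAP 3.4), the number to be randomized and hence an upper limit for the FAS; m = share of infants lacking the covariate, not given in the SAP and assumed to be 5% to 25%; treatment prior Normal(0, 0.7072) on the log odds ratio (SAP 6.5.3). For the prior calculation only, 84 infants per arm (1:1 assumed) and risks of 70% and 50% (the scenario in SAP 3.4).

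Infants lost = 168 × m. Data-based SE factor = 1/√(1 − m).

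Data precision of the log odds ratio at full N:
1 / [1/(84 × 0.7 × 0.3) + 1/(84 × 0.5 × 0.5)] = 1 / (1/17.64 + 1/21) ≈ 9.6.
Prior precision = 1/0.7072² ≈ 2.0.
Posterior SD factor = √[(9.6 + 2.0) / (9.6 × (1 − m) + 2.0)].

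| m | Infants lost | Infants left | SE factor | Posterior SD factor |
|---|---|---|---|---|
| 5% | 8 | 160 | 1.03 | 1.02 |
| 10% | 17 | 151 | 1.05 | 1.04 |
| 15% | 25 | 143 | 1.08 | 1.07 |
| 25% | 42 | 126 | 1.15 | 1.12 |

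These factors leave out the center and encephalopathy terms.

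**Several covariates.** With missing rates m₁ and m₂, the share lost lies between the larger of the two (gaps in the same infants) and m₁ + m₂ (gaps in different infants). For 10% and 5% that is 17 to 25 infants. The gas variables come from the same sample, so their losses largely overlap and sit near the lower end. Covariates from other forms may add to them.

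**Can the estimate move without confounding?** Only if the effect differs by gas availability. As an illustration, assume 20% have no gas, equal control risk in both groups, and RR 0.70 with a gas and 1.0 without. The FAS RR is 0.8 × 0.70 + 0.2 × 1.0 = 0.76, and the complete-case RR is 0.70. With RR 0.70 in both groups, both figures are 0.70 and only precision is lost. The SAP does not support either assumption over the other.

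**The case against.** The strongest reply is that this is a conditional problem in a supporting analysis. Blood gas is one candidate among several dozen and enters only if selected. SAP 6.5.7 makes the sensitivity analysis discretionary, although 6.5.2 and 6.5.5 say it will be done, and limits it to the primary outcome and death. The main model uses only encephalopathy level and center. These are the randomization stratification factors, so they should be known for every infant. All of this stands, and it limits how much weight the point can carry.

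Stronger readings are tempting, but the document does not support them:

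- A reader might infer that everyone entering by the clinical route is lost. That route also takes infants with modest acidemia, who have a gas by definition. Only its no-gas part is exposed, and a cord or first-hour result could still be recorded after screening.
- A reader might infer bias between arms. A cord or first-hour gas is absent before randomization, so the comparison within the reduced sample remains randomized. The shift to 0.70 in the illustration depends on an assumed difference in effect.
- A reader might infer that the loss would be hidden. Section 5.3 requires the amount missing to be tabulated, so each covariate's gaps would be visible, though not the N of a given model.
- A reader might infer that adjustment and sample change can never be told apart. Refitting the encephalopathy-plus-center model on the same complete cases separates them without imputation. The SAP does not plan this refit, and it would not recover the lost precision.

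For discrete covariates, the indicator coding in 6.5.1 could already carry a missing level. The unresolved gap is therefore mainly in continuous covariates.

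**Conclusion.** The point holds as a conditional defect. Section 6.6 as worded cannot be reconciled with the FAS statement in 6.5.7 once an incomplete continuous covariate is selected. The consequence is an adjusted estimate on a smaller, different sample and some loss of precision. It does not cause confounding by arm and has no effect on the main primary result.

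Over an assumed missing share of 5% to 25%, the loss is 8 to 42 of 168 infants, with the data-based SE up by about 3% to 15% and the posterior SD by about 2% to 12%. The true share is not in the document, so the size cannot be fixed further. These figures rest on complete-case deletion being the default and on 168 standing in for the FAS.

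The exposure is greatest for adjusted secondary outcomes, since 6.5.5 leaves no unadjusted fit beside them. It may also reach the subgroup models in 6.5.8, which build on models with added covariates. This is a cheap improvement worth making; it does not threaten the trial's primary conclusion.

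**What to change.** Restrict 6.6 to outcomes and add a rule for covariates measured before randomization:

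- Fill a missing continuous value with the mean of the observed values pooled over both arms (zero after centering), and add a 0/1 missing indicator with the Normal(0, 1) prior that 6.5.3 and 6.5.4 already assign to added covariates.
- Use one shared indicator for all the blood gas variables. Separate indicators would mark nearly the same infants and be close to collinear.
- Give discrete covariates a missing level.
- Fit the adjusted and unadjusted models on the same FAS infants, and report the N used in each.

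The fill-in uses neither outcome nor treatment arm. The cost is a short addition to the SAP, a few lines of code, and one extra model term per incomplete covariate group. If the sponsor prefers to keep the ban on imputation, the minimum is to refit the base model on the complete cases, report the N, and stop describing the adjusted analysis as based on the FAS. That restores comparability but not precision.

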3.7 Timing of Interim and Final Analysis

Final analyses were planned to occur after 168 infants were consented, enrolled, randomized, and followed to 18-22 months corrected age. The study analysis database is constructed using those who died before the 18-22 month follow-up and all survivors not lost to follow-up who underwent protocol-specified neurodevelopmental assessment.

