4.3 Analysis Datasets

This analysis will use two analysis populations, a full analysis set (FAS) and per-protocol (PP).² The FAS analysis population will include all randomized infants with ascertained primary outcomes. This FAS analysis population is recognized as being as close as possible to an intent-to-treat population. All analyses based on the FAS will analyze infants as randomized. The PP analysis population will include all infants who received their randomized treatment (72 hours of hypothermia or normothermia) and have a determined primary outcome. All analyses based on the PP will analyze infants as treated.

² ICH E9: <https://www.fda.gov/regulatory-information/search-fda-guidance-documents/e9-statistical-principles-clinical-trials>

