5.2 Withdrawal / Follow-up

- Infants can be lost-to-follow-up between Network Status (120 days after birth, or time of discharge/transfer) and the time of the scheduled 18-22-month follow-up visit (although the Covid pandemic did require some subjects to undergo follow-up at later dates). The Premie Hypothermia PH13 form is completed at the time of network status. Infants cannot be lost prior to network status.
- Infants who withdraw from the study will not have any data collected beyond the timepoint of withdrawal. Data collected prior to withdrawal will be available for summarization and analysis.
- Numbers of infants who withdraw or are lost to follow-up will be presented in the CONSORT diagram.

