6.5.5 Final Analysis

The final analysis will occur after 168 infants have completed the trial, as specified earlier. The final analysis will not occur until all enrolled infants have a primary outcome determination, i.e. have the primary endpoint value assigned, classified as withdrawn without primary outcome assigned, or deemed lost to follow-up. Part of determining primary outcome of enrolled infants will involve masked adjudication of outcomes for infants who have an indeterminable outcome based on partially collected follow-up information. Once all enrolled infants have reached final status and primary endpoints determined, the clinical database will be exported, and study analysis datasets created. At that point, the analysis datasets will be considered “locked” and any further adjustments to the clinical datasets will not be included in the analysis datasets.

The final analysis will involve posterior distribution estimation for the effect of hypothermia relative to normal cooling. For binary outcomes, the effect will be the adjusted relative risk and adjusted risk differences calculated from a binomial regression model with logit link and post processing of

predicted outcome probabilities. For count outcomes, the effect will be the adjusted relative risk from the two groups obtained using negative binomial regression. For ordinal outcomes, the effect will be the adjusted odds ratio calculated from the cumulative logits.

For treatment relative risk estimation, posterior probabilities of >0%, >5%, >10% and >20% decrease in binary outcomes will be calculated. If θ is the relative risk defined as risk in cooling group over risk in control group, then the above specified posterior probabilities are, $\Pr(\theta < 1 | X)$, $\Pr(\theta < 0.95 | X)$, $\Pr(\theta < 0.9 | X)$, $\Pr(\theta < 0.8 | X)$. In addition to posterior probability calculations, graphical displays of the posterior distribution and appropriate 95% credible intervals for the over-all relative risk will be created. Finally, forest plots of the center level relative risks and 95% credible intervals will be created.

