In addition to adjusting for level of encephalopathy and center in the logistic model, the final analysis of the primary outcome will also perform sensitivity analyses concerning possible treatment effect confounders present at randomization. These sensitivity analyses will adjust for potential treatment effect confounders in addition to adjusting for level of encephalopathy and center. The additional covariates will be determined by comparing the primary outcome with respect to baseline characteristics listed in Section 5.3. More details about these sensitivity analyses are given in section 6.5.7. Secondary analyses may also adjust for covariates, but in such a case the analysis will only be completed with covariate adjustment. No secondary analyses will be completed twice,

in the sense of one analysis without covariates and another analysis with covariates. These analyses will use the FAS population.

The lack of preexisting data suggests that the neutral prior distribution may be most appropriate for presentation of final results of risk differences; however, generation of final results of the primary outcome analysis using the skeptical (OR of 1.10) and enthusiastic priors (OR of 0.75) will also be produced for the primary outcome to give a broad overview of the implications of the trial's efficacy results. Note, these priors are expressed on the OR scale, because the underlying model is a logistic regression model and posteriors of risk difference will be generated via post-processing. Skeptical, neutral, and enthusiastic priors will also be utilized in the analysis of primary outcome components. All non-primary or non-primary component outcomes will be analyzed using only the neutral prior.

For treatment rate ratios of count outcomes estimation, the posterior of the treatment rate ratio, ϕ , will be graphically illustrated and summarized by calculating the median treatment rate ratio, the 95% credible interval of treatment rate ratio, and $\Pr(\phi < 1 | X)$ using neutral priors. These analyses will use the FAS population.

Primary Analysis of Primary Outcome

With respect to the primary outcome, the data will be analyzed using the FAS population.

In summary the following analyses will be completed on the primary outcome:

Population	FAS					
Treatment effect	RR			RD		
Prior*	E	N	S	E	N	S

* E = Enthusiastic, N = Neutral, S = Skeptical

Each of the six analyses of the primary outcome will generate the following results:

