- Posterior plot of treatment effect
- Posterior median and posterior standard deviation
- 95% credible interval
- For relative risk, posterior probabilities of >0%, >5%, >10%, and >20% decrease in the primary outcome will be calculated
- For risk difference, posterior probabilities of >0%, >1%, >2%, >3%, and >5% decrease in primary outcome will be calculated
- forest plot of the center level effect and 95% credible intervals.

If the FAS analysis of the primary outcome results in any clinically notable findings, then the primary outcome may also be analyzed in an exploratory fashion using the PP population.

Analysis of Secondary Outcomes

With respect to secondary outcomes, analyses will follow the same process as the primary outcome analysis defined above. See MockTablesAppendix.docx for list of selected variables.

Analysis of Safety (AE) and Hospital Outcomes

Safety and hospital outcomes listed in Sections 6.2 and 6.3 will be analyzed using the FAS population and if necessary, the PP population using relative risk models, proportional odds models, or Negative Binomial models, depending on the type of outcome.

With respect to binary safety outcomes, the estimated posterior distribution of relative risk, θ , based on the data and the neutral prior will be used to determine posterior probabilities of harm from the intervention, $\Pr(\theta > 1 | X)$, as well as 95% credible intervals.

For ordinal safety outcomes, the estimated posterior distribution odds ratio for the cumulative logits, ϕ , will be estimated based on the data and the neutral prior. In addition, posterior probabilities of harm, $\Pr(\phi > 1 | X)$, and 95% credible intervals of ϕ will be calculated.

For count type safety outcome, the estimated posterior distribution of the treatment mean rate, ϕ , will be estimated based on the data and the neutral prior. In addition, posterior probabilities of harm, $\Pr(\phi > 1 | X)$, and 95% credible intervals of ϕ will be calculated.

Analysis of Ultrasound, CT scan, MRI and encephalopathy outcomes

Ultrasound, CT scan, MRI, and encephalopathy outcomes will be analyzed using the FAS population. Head ultrasounds, CT scans, and brain MRIs will be summarized by treatment and time (prior to intervention, during intervention, after intervention, any time). Summaries will be created for number of babies with any abnormal findings during time period data recorded, and for total events across all babies during any time period.

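### Safety and hospital outcomes are analysed only in infants with an 18-22 month outcome, and the complete-case primary analysis has no check on missing outcomes

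*SAP*

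**What the plan says.** Section 4.3 defines the population by outcome availability: "The FAS analysis population will include all randomized infants with ascertained primary outcomes". Section 3.7 describes the same selection from the database side: it holds "those who died before the 18-22 month follow-up and all survivors not lost to follow-up who underwent protocol-specified neurodevelopmental assessment". Section 6.5.5 applies this population to the composite ("With respect to the primary outcome, the data will be analyzed using the FAS population") and also to short-term outcomes: "Safety and hospital outcomes listed in Sections 6.2 and 6.3 will be analyzed using the FAS population".

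Missing outcomes have two sources in Section 5.2. The first is loss to follow-up, with a lower time limit: "Infants cannot be lost prior to network status". The second is withdrawal, with no such limit: "Infants who withdraw from the study will not have any data collected beyond the timepoint of withdrawal". The same section says that data gathered before withdrawal may be used.

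Section 6.6 is one sentence: "No imputation for missing data will be done". The sensitivity analyses in Sections 6.5.5 and 6.5.7 adjust for baseline covariates, with an optional exploratory per-protocol analysis. The per-protocol set also requires a known primary outcome (Section 4.3), so it cannot test the effect of missing ones. The one step that recovers outcomes, in Section 6.5.5, is "masked adjudication of outcomes for infants who have an indeterminable outcome based on partially collected follow-up information".

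**The concern.** There are two consequences.

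The first concerns short-term safety, which is primary objective 2 in Section 2.2. Its window closes 108 hours after baseline, and hospital outcomes close at death or discharge. Infants lost later have already supplied these data, as may some who withdraw. Excluding them makes safety denominators depend on attendance about two years later. Only infants not known to have died can be excluded this way, so death, and any event commoner in infants who die, is over-represented.

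The second concerns the composite. It is known for every recorded death but, among survivors, only for those assessed or adjudicated. Missingness is therefore tied to one component of the outcome. The trial is unmasked (Section 3.1), so loss or withdrawal could differ by arm. The main result is a posterior probability and an interval for the RR and risk difference, and the plan gives the reader no way to see how far these depend on the infants left out.

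**Working it through.** **Inputs.** From the SAP: planned control risk of at least 70% and 168 infants (Section 3.4); neutral log odds ratio prior with mean 0 and SD 0.7072 (Section 6.5.3). The SAP states no mortality, disability or loss rate, so there is no figure of its own to reproduce here. Assumed: 84 infants per arm (1:1 allocation), mortality d = 20%, share of survivors lost L = 5% to 20%. Composite risk p is set at 70% (planning rate) and at 44% (20% death plus 30% disability in the 80% who survive).

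**Step 1: in-hospital death in the FAS.** Observed mortality = d / [d + (1 − d)(1 − L)].
- L = 10%: 0.20 / (0.20 + 0.80 × 0.90) = 0.20 / 0.92 = 21.7%.
- No loss in one arm and L = 20% in the other: 0.20 against 0.20 / 0.84 = 23.8%. A true RR of 1.00 for in-hospital death becomes 0.84 or 1.19, depending on which arm loses infants.

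**Step 2: composite, if lost survivors resemble followed survivors.** Observed risk = [d + (p − d)(1 − L)] / [d + (1 − d)(1 − L)].
- p = 70%, L = 10%: (0.20 + 0.50 × 0.90) / 0.92 = 70.7%.
- p = 70%, L = 20%: (0.20 + 0.50 × 0.80) / 0.84 = 71.4%.
- p = 44%, L = 10%: (0.20 + 0.24 × 0.90) / 0.92 = 45.2%.
- p = 44%, L = 20%: (0.20 + 0.24 × 0.80) / 0.84 = 46.7%.

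With no true effect:

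| True risk in both arms | Risk at equal 10% loss | RR at 5% vs 15% loss | RR at 0% vs 20% loss | Pr(benefit) at 0% vs 20% |
|---|---|---|---|---|
| 70% | 70.7% | 0.99 or 1.01 | 0.98 or 1.02 | 0.57 or 0.43 |
| 44% | 45.2% | 0.97 or 1.03 | 0.94 or 1.06 | 0.62 or 0.38 |

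The last column is a normal approximation with 84 infants in one arm and 84 × 0.84 = 70.6 in the other. At 44% the log odds ratio is −0.108 with SE 0.32. The prior gives it weight w = 0.7072² / (0.7072² + 0.105) = 0.83, and Φ(0.108 / 0.324 × √0.83) = 0.62. At 70% the log odds ratio is −0.069, SE 0.355, w = 0.80, giving 0.57. Without loss the value is 0.50.

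Across d = 10% to 40% and L = 5% to 20%, a 70% risk reads 70.2% to 72.7%.

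**Step 3: direction.** Let mL be the disability rate in lost survivors. Observed risk = [p − (1 − d)L × mL] / [1 − (1 − d)L]. With p = 70%, d = 20%, L = 10% this is (0.70 − 0.08 × mL) / 0.92:
- mL = 0: 76.1%
- mL = 62.5% (the rate in all survivors, 0.50 / 0.80): 70.7%
- mL = 70%: 70.0%
- mL = 100%: 67.4%

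The bias is zero when mL equals the overall composite risk and negative above it.

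**Step 4: bounds without an assumption on the lost infants.** Suppose 13 of 84 are missing per arm, with 36 events in 71 hypothermia infants and 50 in 71 controls. The complete-case RR is 36 / 50 = 0.72. Best case for hypothermia: 36 / (50 + 13) = 0.57. Worst case: (36 + 13) / 50 = 0.98. With 8 missing per arm (38 and 53 events in 76 each), 0.717 spans 38 / 61 = 0.62 to 46 / 53 = 0.87.

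**The case against.** The plan does guard against missing outcomes. Adjudication is masked. A footnote to Section 6.1 asks the programmer to trace and document the cause of each missing value, later visits are accepted because of the pandemic, and the CONSORT diagram will count losses and withdrawals. Section 4.3 is open that its set only approximates intent-to-treat. At the SAP's own 70% risk the shifts in the composite are small. Even the 0% against 20% case at 44% risk gives a probability of benefit of 0.62 under the null, below the 0.80 used in the Section 3.4 simulations. All of this stands and limits the size of the point. It does not meet it, because adjudication needs some follow-up data, and counting losses does not show what they do to the estimate.

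A reader might infer more than the SAP supports in three ways:
- **That event rates are biased upward as a matter of fact.** Step 3 shows that the direction depends on disability among the lost infants, about which the SAP says nothing.
- **That loss differed between arms.** No passage says so. The design leaves room for it, and the plan has no check.
- **That every missing outcome belongs to an infant who reached network status.** This is true of losses but not necessarily of withdrawals.

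It can also be said that the safety question concerns the choice of population and not imputation. That is right, and it is why it has a separate remedy. The statement in Section 5.2 that pre-withdrawal data may be used does not settle it, because Section 6.5.5 still names the FAS.

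**Conclusion.** The point holds in two parts.

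The clearer part is safety. As written, the rule removes infants with complete 108-hour and hospital data from primary objective 2, and this can be avoided with data already collected. An in-hospital mortality of 20% would read 21.7% at 10% survivor loss.

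For the composite, the defect is that the complete-case rule is untested. Upward bias is the expected direction only if lost survivors resemble those followed. Equal loss of that kind moves rates by at most about 3 percentage points in the range examined. The larger exposure is loss that differs by arm or depends on disability: a null RR of about 0.98 (70% risk) or 0.94 (44% risk) at 0% against 20% loss, and much wider best/worst-case bounds. Every size rests on assumed mortality, loss and equal allocation. None is an estimate of what happened in this trial.

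**What to change.** 1. **Safety and hospital outcomes.** In Section 6.5.5, analyse 108-hour safety, hospital course and in-hospital death in all randomized infants with those data, as randomized. Death by 18-22 months cannot be treated this way, because the later vital status of lost infants is unknown. It belongs under item 2.
2. **Composite.** Keep the FAS analysis as primary. In Section 6.5.7, prespecify a best/worst-case or tipping-point table by arm in all randomized infants.
3. **Optional.** Multiply impute disability for infants with missing outcomes, using arm, encephalopathy level, discharge examination and MRI in a separate imputation model, then fit the planned logistic model unchanged. The discharge examination and MRI are post-randomization and should not enter the treatment-effect model. This imputation takes lost infants as alive, so it supplements item 2 and does not replace it.
4. **Section 6.6.** Reword so that the ban on imputation applies to the primary analysis only.

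The cost is revised wording, a few model runs on data already collected, and extra output to explain, including safety denominators that differ from those of the composite. Added after results are known, these analyses would count as ad hoc under Section 6.5.9.
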